The Role of the Renin-Angiotension System in Pediatric Essential Hypertension
PI [name], MS

Background

Pediatric essential hypertension is increasingly common, occurring in 5-10% of normal-weight children and up to 25% of children with obesity. It is a risk factor for adult cardiovascular and renal disease. But even during childhood, hypertension is associated with significant morbidity, including cognitive impairment and organ damage. In the heart and kidneys, this organ damage is characterized by thickened heart muscle (left ventricular hypertrophy) and spillage of protein in the urine (albuminuria). Obese children are also at risk for fatty liver disease. However, the cause of pediatric essential hypertension, the role of obesity, and the mechanisms behind heart and kidney injury are poorly understood. Due to these limitations, there are no first-line medications, and treatment is often inadequate. An altered renin-angiotensin system may cause pediatric essential hypertension and organ damage. Evidence suggests uric acid, FGF23, and obesity play a role in renin-angiotensin system-mediated injury. An improved comprehension of the pathophysiology of pediatric essential hypertension could enhance clinical care by targeting treatment to the cause of disease and informing novel measures of organ damage.

Specific Aims

The **goal** of this proposal is to begin to elucidate the origins of pediatric essential hypertension and determine how it causes cardiac and renal disease. Our **primary hypothesis** is that an altered renin-angiotensin system leads to the development of pediatric essential hypertension and organ damage in the heart and kidney, specifically left ventricular hypertrophy and albuminuria. We postulate that a relative increase in angiotensin (Ang) II tone compared to Ang-(1-7) tone in the circulation and the kidney (measured in the plasma and urine, respectively) leads to disease. Our **secondary hypotheses** are that abnormalities in renin-angiotensin system tone are related to higher uric acid and FGF23 and, with concurrent obesity, contribute to nonalcoholic fatty liver disease. We propose to test our hypotheses by recruiting 100 subjects aged 5-17 years who are referred for a new diagnosis of pediatric essential hypertension to the Pediatric Nephrology clinic at Brenner Children's Hospital. Our **Specific Aims** are to:

Aim 1: Determine the associations among the Ang II:Ang-(1-7) ratio, blood pressure, left ventricular hypertrophy, and albuminuria at baseline and after 12 months of treatment in incident cases of pediatric essential hypertension.

Hypothesis 1: *An increased ratio of Ang II to Ang-(1-7) is associated with higher blood pressure, left ventricular hypertrophy, and albuminuria at baseline and at 12 months.*

Aim 2: Investigate the relationships between the Ang II:Ang-(1-7) ratio and additional markers of cardiovascular and renal disease including uric acid and FGF23 to further elucidate the mechanisms behind the renin-angiotensin system's role in organ damage.

Hypothesis 2: *An increased ratio of Ang II to Ang-(1-7) is correlated with uric acid and FGF23.*

Aim 3: Assess the association between the Ang II:Ang-(1-7) ratio and nonalcoholic fatty liver disease, defined by elevated liver enzymes and hepatic fat infiltration on ultrasound, to investigate the role of the renin-angiotensin system in obesity-associated organ damage.

Hypothesis 3: *An increased ratio of Ang II to Ang-(1-7) is associated with elevated aspartate aminotransferase and alanine aminotransferase and hepatic fat infiltration on ultrasound.*

Study Design

Primary Study Subjects - Subjects between the ages of 5 and 17 years who are referred for a new diagnosis of hypertension will be recruited over one year from the tertiary care Pediatric

Nephrology clinic at Brenner Children's Hospital. We will obtain parental consent and subject assent. Inclusion criteria include a diagnosis confirmed with three separate blood pressure measurements $\geq 95\text{th}$ percentile for age, sex, and height. Exclusion criteria include secondary causes such as renovascular hypertension and renal disease. The clinic sees approximately 20 new hypertension patients a month, and we anticipate enrolling 100 patients within the one-year study period. The target population is diverse (approximately 40% black, 40% white, and 20% Hispanic), predominantly male (60%), and 50% obese. Each subject will undergo a thorough evaluation per the standard of care. After baseline study assessment, subjects will be started on an antihypertensive medication per the standard of care by an independent clinician not involved in the study. Subjects will be seen in the clinic every three months per standard of care to obtain labs, monitor their blood pressure, and adjust their medication (see **Figure 1** below). Subjects will be evaluated at 12 months with repeat measurements of the outcomes.

Control Arm 1 – Ten healthy normotensive subjects between the ages of 5 and 17 years will be recruited from a general pediatrics clinic (Cornerstone Pediatrics, part of the Wake Forest Baptist Health system) to obtain samples for measurements of the following outcomes for comparison with the hypertensive participants over the same age range: left ventricular hypertrophy on echocardiograms, urine albumin, uric acid in the blood, FGF23 in the blood, and klotho in the blood and urine, as well as the predictors angiotensin II and angiotensin-(1-7) measured in the blood and urine.

Control Arm 2 – Fifty normotensive subjects with obesity between the ages of 5 and 17 years will be recruited from the Brenner FIT program or the Gastroenterology clinic under the direction of my collaborator [name], who is an associate professor of Pediatric Gastroenterology and the Director of Brenner FIT. Eligible patients will be approached about the study by their physician. Control Arm 2 subjects will undergo measurement of the following outcomes: fatty liver disease on ultrasound, liver function testing (AST, ALT), and uric acid in the blood, all of which are obtained as standard of care. They will also undergo collection of angiotensin II and angiotensin –(1-7) in the blood and urine at the same time as clinical samples are obtained.

We will obtain parental consent and subject assent for all control subjects. Exclusion criteria include any significant medical problems or current treatment with an antihypertensive medication. Control subjects in both arms will be evaluated at baseline and at one year with only blood pressure measurements and blood and urine for collection of angiotensin II, angiotensin-(1-7), FGF23, and klotho.

Data Collection

Clinical data will be collected from the electronic medical record, including height, weight, age, sex, parent-reported race, and past medical and family histories. We will calculate body mass index and define overweight/obesity as a body mass index $\geq 85\text{th}$ percentile for age and sex. We will note antihypertensive medication type and dosage. We will calculate the estimated glomerular filtration rate to measure renal function standardized to age, sex, and height. All data will be de-identified and stored securely in an encrypted system.

Laboratory Assessment

Study Subjects - Blood (less than 5 mL) and urine samples will be collected at baseline and every three months up to 12 months at the same time as routine clinical labs at the Brenner Children's Hospital Clinic laboratory or the Downtown Health Plaza laboratory, so as to avoid additional study-specific blood draws. These samples will be sent to the Clinical Research Unit for processing. The predictors Ang II and Ang-(1-7) will be measured in the plasma and urine

using radioimmunoassays in a CLIA-certified laboratory within the Biomarker Analytical Core. We will calculate the ratio of the two peptides and, in the urine, standardize their values to urine creatinine. Uric acid, aspartate aminotransferase, alanine aminotransferase, lipid profile, creatinine, urine albumin, and urine creatinine will be collected per standard of care and analyzed in the clinical laboratory. FGF23 will be measured by ELISA (Immutopics, San Clemente, CA) in the Core. We will bank de-identified and securely-stored blood and urine samples for future analysis.

Control Subjects – Blood (less than 5 mL) and urine samples will be collected from all control subjects at the Brenner Children’s Hospital Clinic laboratory. The predictors Ang II and Ang-(1-7) will be measured in the plasma and urine using radioimmunoassays in a CLIA-certified laboratory with the Biomarker Analytical Core. We will calculate the ratio of the two peptides and, in the urine, standardize their values to urine creatinine. Uric acid, aspartate aminotransferase, alanine aminotransferase, lipid profile, creatinine, urine albumin, and urine creatinine will be collected per standard of care and analyzed in the clinical laboratory. FGF23 will be measured by ELISA (Immunotopic, San Clemente, CA) in the Core. Klotho will be measured by ELISA (IBL, MN) in the Core. We will bank de-identified and securely-stored blood and urine samples for future analysis.

Imaging

Study Subjects - All patients seen in our clinic for pediatric essential hypertension receive baseline and follow-up echocardiograms to evaluate for left ventricular hypertrophy. Patients with obesity receive baseline and follow-up ultrasounds of the liver to evaluate for hepatic fat infiltration. Imaging studies are interpreted by pediatric cardiologists and radiologists at Brenner Children’s Hospital.

Control Arm 1 – Subjects (10 subjects) will have baseline echocardiograms to evaluate for left ventricular hypertrophy. Imaging studies are interpreted by pediatric cardiologists and radiologists at Brenner Children’s Hospital.

Control Arm 2 – Subjects (50 subjects will have baseline ultrasounds of the liver to evaluate for hepatic fat infiltration as part of the standard of care. Imaging studies are interpreted by pediatric cardiologists and radiologists at Brenner Children’s Hospital.

Blood Pressure Measurements

Blood pressure will be measured at clinic visits per standard guidelines. Because age, sex, and height define normative pediatric values, we will standardize blood pressure with z scores. Continuous blood pressure (measured in clinic for 10 minutes) will be collected at the baseline and 12-month visits. Ambulatory blood pressure monitoring will be employed at baseline and at 12 months per clinical practice and has been validated in patients as young as five years old. Subjects wear a monitor (Spacelabs 90207, Redmond, WA) at home for 24 hours; the monitor records a minimum of one valid blood pressure an hour. Parameters include i) mean blood pressure and ii) blood pressure load (percent of readings $\geq 95^{\text{th}}$ percentile) for the wake, sleep, and 24-hour periods; and iii) percent nocturnal dipping (percent drop in sleep mean blood pressure from wake mean BP). Ambulatory blood pressure index will be calculated as the mean divided by the 95th percentile. All parameters will be referenced to normal values. Clinic blood pressure will be measured at the study visit per standard guidelines for all control subjects at baseline and at one year. In Control Arm1, continuous blood pressure (measured noninvasively in clinic for 10 minutes) and ambulatory blood pressure monitoring will be assessed in control subjects at baseline.

Outcomes

The primary outcomes are blood pressure, left ventricular hypertrophy, and albuminuria at baseline and after 12 months of treatment. Blood pressure will be measured in clinic, by continuous blood pressure, and by ambulatory blood pressure monitoring. A left ventricular mass index $\geq 95\text{th}$ percentile for age and sex on echocardiography defines left ventricular hypertrophy, and a urinary albumin-to-creatinine ratio $> 30 \text{ mg/g}$ creatinine defines albuminuria. The secondary outcomes are serum uric acid, plasma FGF23, and nonalcoholic fatty liver disease, defined by elevated aspartate aminotransferase and alanine aminotransferase and hepatic fat infiltration on ultrasound of the liver with elastography.

[figure not shown]
Statistical Plan

Summary statistics will include frequency distributions, mean with standard deviation, and median with interquartile range. Natural logarithmic transformation will improve continuous variable distributional characteristics as indicated. Chi-square and Fisher's exact tests, t-test, and Wilcoxon Rank-Sum test will evaluate between-group comparisons. Pearson or Spearman correlation coefficients will assess for continuous variable correlations. Bivariate analyses will identify potential confounders of the relationships between the predictors and the outcomes.

We will use general linear and logistic regression models to evaluate the relationships between the predictors and outcome measures. *A priori* covariates include sex and race given their relationships with the RAS and the outcomes. We will investigate potential effect modifiers by employing interaction terms and stratifying analyses. A potential confounder will be included in the multivariate models if i) there is an association between the predictor and outcome at $p < 0.2$, or ii) there is a $> 10\%$ change in the regression coefficient for the predictor-outcome relationship. Covariates will be retained in the final model if $p < 0.05$. A two-sided alpha of 0.05 will be considered statistically significant. We will use Enterprise Guide, Version 7.11 of the SAS System for Windows (SAS Institute Inc., Cary, NC) for all analyses.

Sample Size and Power

With 100 subjects we will have $> 90\%$ power to detect a correlation as low as 0.4 between Ang II and Ang-(1-7) and blood pressure. Based on previous data, we estimate the prevalence of left ventricular hypertrophy is 40-60% before and 10-20% after treatment. We estimate the plasma ratio of Ang II to Ang-(1-7) is at least 7.7 (standard deviation 8.4). Therefore, we will have $> 90\%$ power to detect an odds ratio of 1.15 or higher both at baseline and at one year. The prevalence of albuminuria is 20-60%; therefore the effect size and power we can achieve with 100 subjects will be similar to that achieved for left ventricular hypertrophy.

References

1. The Fourth Report on the diagnosis, evaluation, and treatment of high blood pressure in children and adolescents. *Pediatrics* 2004; 114(Supplement 2):555-576

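### Age is not a fixed covariate across ages 5-17, so an unadjusted Aim 2 correlation can reflect shared age trends, and the p<0.05 retention rule can drop age from the regressions

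*Protocol*

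**What the plan says.** Under Specific Aims, the protocol plans on "recruiting 100 subjects aged 5-17 years who are referred for a new diagnosis of pediatric essential hypertension". Hypothesis 2 reads "An increased ratio of Ang II to Ang-(1-7) is correlated with uric acid and FGF23".

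The Statistical Plan states that "Pearson or Spearman correlation coefficients will assess for continuous variable correlations" and names no partial or adjusted correlation. For the regressions, the a priori "covariates include sex and race given their relationships with the RAS and the outcomes". Any other confounder enters through a screen (p<0.2, or a change of more than 10% in the coefficient of interest), and covariates stay in the final model only if p<0.05. No exemption from that rule is stated for sex and race.

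Elsewhere the protocol treats age as important. Blood Pressure Measurements says: "Because age, sex, and height define normative pediatric values, we will standardize blood pressure with z scores". Outcomes references left ventricular mass index to age and sex. Data Collection references body mass index to age and sex, and estimated glomerular filtration rate to age, sex and height. No age reference is given for the peptide ratio, uric acid or FGF23, nor for what counts as elevated AST or ALT. Urine peptides are standardised to creatinine, but that divisor cancels in a ratio from one sample and does not adjust for age. Age is collected; pubertal stage is not listed.

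**The concern.** Aim 2 is meant to throw light on the mechanism of organ damage. In a cohort running from 5 to 17 years, two quantities that both drift with age will correlate across children even when neither acts on the other. A significant unadjusted coefficient could then be reported as support for a link between the renin-angiotensin system and uric acid or FGF23. Opposing age trends would do the reverse and mask a real link.

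The regressions have some protection through the confounder screen, but whether age stays in depends on its own p-value. That is a test of whether age predicts the marker, not of whether leaving age out biases the ratio's coefficient.

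**Working it through.** **Inputs.** From the protocol: n = 100 (Specific Aims; Sample Size and Power), ages 5-17 (Study Design), and "A two-sided alpha of 0.05 will be considered statistically significant" (Statistical Plan). The correlations of age with the ratio and with the marker are assumptions, because the protocol gives none.

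**Step 1: the protocol's own power figure.** Sample Size and Power claims more than 90% "power to detect a correlation as low as 0.4 between Ang II and Ang-(1-7) and blood pressure". By Fisher's z,

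power = Φ(atanh(r)·√(n−3) − 1.960) + Φ(−atanh(r)·√(n−3) − 1.960).

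With r = 0.4 and n = 100: atanh(0.4) = 0.4236, √97 = 9.849, product 4.172, and 4.172 − 1.960 = 2.212. The power is 98.7%, so the claim holds. It is stated for blood pressure, which is age-standardised; no counterpart is given for uric acid or FGF23. At n = 100 any |r| of about 0.197 or more is significant.

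**Step 2: correlation induced by age alone.** With no link between ratio and marker other than age,

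induced r = r(age, ratio) × r(age, marker).

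Putting the induced r into the Step 1 formula gives the false-positive rate of the unadjusted test. For 0.3 and 0.4: r = 0.12, atanh = 0.1206, times 9.849 = 1.188, and 1.188 − 1.960 = −0.772. The upper tail is 22.0% and the lower tail about 0.1%, together 22.1%.

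| r(age, ratio) / r(age, marker) | induced r | unadjusted false positives |
|---|---|---|
| 0 / 0.5 | 0 | 5% |
| 0.2 / 0.3 | 0.06 | 9.1% |
| 0.3 / 0.4 | 0.12 | 22.1% |
| 0.4 / 0.5 | 0.20 | 51.5% |
| 0.4 / 0.2 | 0.08 | 12.4% |
| 0.5 / 0.2 | 0.10 | 16.7% |

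**Step 3: regressions under the protocol's selection rule.** This was simulated at n = 100 with 4,000 or 5,000 trials per scenario. Sex and race were always in the model and had no effect. Age entered if p<0.2 with both ratio and marker, or if it changed the ratio's coefficient by more than 10%, and was then kept only if its own p<0.05. Ranges are results from repeated runs.

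| r(age, ratio) / r(age, marker) | false positives under the rule | trials in which age is kept |
|---|---|---|
| 0 / 0.5 | 4.5% | 89% |
| 0.2 / 0.3 | 5.5% | 81% |
| 0.3 / 0.4 | 5.2-5.6% | 98% |
| 0.4 / 0.5 | 4.8-5.4% | 99.8% |
| 0.4 / 0.2 | 9-10% | 45% |
| 0.5 / 0.2 | 11.4-12.6% | 40-41% |

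A model with sex and race alone does no better than the unadjusted correlation (for example 22% at 0.3/0.4 and 17% at 0.5/0.2). With age forced in, the rate was 4.2% to 5.3% in every scenario in which that model was run.

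**Step 4: why the last two rows differ.** The bias depends on the product of the two age correlations, but the retention rule tests only the association of age with the marker. When that is modest (0.2) and the association with the ratio is larger, age fails p<0.05 in more than half of trials and its bias stays in the model.

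**The case against.** The strongest reply is that the plan already adjusts. Aim 2 speaks of relationships, uric acid and FGF23 are listed as secondary outcomes, and the Statistical Plan assigns regression to predictor-outcome relationships. The Pearson/Spearman sentence sits among descriptive and bivariate methods, and nothing names the plain coefficient as the test of Hypothesis 2. Within the range 0.2/0.3 to 0.4/0.5 the screen brings the regressions to about 5%. This stands: a reader might take 9-52% as the error rate of the whole plan, and it is not. It applies only to an unadjusted correlation, which the wording of Hypothesis 2 nevertheless invites.

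Second, confounding needs the ratio itself to vary with age. The documents do not show this, and a ratio may cancel a shared trend. This also stands, so the point is conditional.

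Third, Aim 3 might be read as correlating the ratio with raw enzyme values in the same way. The protocol does not support that. Hypothesis 3 concerns elevated enzymes and fat on ultrasound, which points to the regression models with the screen. No size was computed for it.

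Fourth, the a priori list is not worded as closed, and a separate analysis plan could add age. This carries less weight: the protocol itself sets the named covariates, the entry rule and the retention rule, and age falls under the data-driven part. Entry rule (i), read literally, also refers to the association of the predictor with the outcome rather than to the confounder. The simulation used the more favourable reading.

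**Conclusion.** The point holds for Aim 2 in a conditional form. If both the ratio and the marker vary with age, an unadjusted correlation at n = 100 has a false-positive rate of about 9% (0.2/0.3) to 52% (0.4/0.5); if the ratio is unrelated to age it stays at 5%. The regressions are largely protected (about 4-6% in those scenarios), except where age is tied more to the ratio than to the marker, where about 10-12% remains because age is often dropped.

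For Aim 3 the missing fixed age term is the same omission, but its size is not established. A reader might also infer that growth and puberty alone would produce the hypothesised findings. The protocol gives no age trend for the ratio or the markers, so it supports only that they could. No figure stated in the protocol is wrong, and the aims concerned are secondary. The change is still worth making, since it removes a possible bias at almost no cost.

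**What to change.** In the Statistical Plan:

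- Add age to sex and race as a forced covariate in models whose outcome is not already age-standardised: uric acid, FGF23 and the Aim 3 liver models.
- State that these a priori covariates are exempt from the p<0.05 retention rule.
- State that Hypothesis 2 is tested by the partial correlation, or the regression coefficient, adjusted for age, sex and race. Plain correlations can remain as description.

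The cost is a few sentences and one degree of freedom per model. Age is already collected. The change does not deal with pubertal stage, which is not listed among the data collected; any report of Aim 2 should name that as a limit.

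### Controls are barred for any significant medical problem but cases only for secondary causes of hypertension, so the comparison with Control Arm 1 can include effects of illness admitted only among cases

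*Protocol*

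**What the plan says.** The two eligibility rules are in the protocol's Study Design section.

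- **Cases** (Primary Study Subjects): "Exclusion criteria include secondary causes such as renovascular hypertension and renal disease". No exclusion for other illness is stated.
- **Controls, both arms** (the paragraph after Control Arm 2): "Exclusion criteria include any significant medical problems", and also being on antihypertensive treatment.

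Control Arm 1 is described as follows: "Ten healthy normotensive subjects between the ages of 5 and 17 years will be recruited from a general pediatrics clinic". Its measurements are taken "for comparison with the hypertensive participants over the same age range", and cover LVH on echocardiography, urine albumin, uric acid, FGF23, klotho and the two angiotensin peptides.

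Control Arm 2 is 50 normotensive children with obesity, who "will be recruited from the Brenner FIT program or the Gastroenterology clinic". The protocol lists what is measured in them but does not spell out a comparison with cases. They have liver ultrasound and no echocardiogram.

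The Statistical Plan assigns between-group comparisons to chi-square, Fisher's exact, t and Wilcoxon rank-sum tests. Covariates appear only in the regression models that relate predictors to outcomes. Data Collection records "past medical and family histories" from the electronic record.

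**The concern.** Take a child with diabetes, or with a heart or liver disorder that does not cause hypertension. Under the stated rules this child may be enrolled as a case but not as a control. If the disorder affects left ventricular mass, albuminuria, uric acid or another compared marker, part of the difference between cases and Arm 1 reflects that disorder and not hypertension. More subjects would not remove it, and the unadjusted tests do not correct for it.

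The controls supply the only contrast between hypertensive and normotensive children. That contrast bears on the protocol's broader hypothesis about how pediatric hypertension and its organ damage arise, which associations within cases cannot address alone.

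**Working it through.** **1. What is not touched.** Sample Size and Power uses the 100 hypertensive subjects only, and its claim of more than 90% power reproduces.

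- Correlation of 0.4, N = 100, two-sided alpha 0.05 (Fisher z): Φ(atanh(0.4) × √97 − 1.96) = 98.7%.
- Odds ratio of 1.15, taken per unit of the peptide ratio with SD 8.4: Φ(√(100 p(1−p)) × ln(1.15) × 8.4 − 1.96). This gives 94.1% at 10% LVH, 99.7% at 20%, and above 99.9% at 40-60%.

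No control enters these figures. Aim 1 is likewise set within incident cases.

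**2. Possible size of the bias against Arm 1.** The protocol gives no rate of other illness in cases, so the inputs here are assumptions. Let q be the share of cases with an illness that would have barred a control, and k the shift in a continuous marker in SD units. With no such illness among controls, the bias is q × k.

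For 100 cases and 10 controls the standard error is √(1/100 + 1/10) = 0.332 SD. With no true difference, the chance of a significant result is 1 − Φ(1.96 − qk/0.332) + Φ(−1.96 − qk/0.332), by normal approximation.

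| q | k (SD) | Bias (SD) | Nominal 5% becomes |
|---|---|---|---|
| 0% | any | 0 | 5.0% |
| 5% | 0.5 | 0.025 | 5.1% |
| 10% | 0.5 | 0.05 | 5.3% |
| 10% | 1 | 0.10 | 6.0% |
| 20% | 0.5 | 0.10 | 6.0% |
| 20% | 1 | 0.20 | 9.3% |
| 30% | 1 | 0.30 | 14.8% |

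Over the 10-20% range the bias is 0.05-0.20 SD, or 0.05/0.332 = 0.15 to 0.20/0.332 = 0.60 standard errors. LVH is a yes/no outcome, so these SD figures do not carry over to it directly.

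**3. Cost of removing affected cases, taking 20 of 100.**

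- Against Arm 1: √(1/80 + 1/10) = 0.335 against 0.332, about 1% wider.
- Against Arm 2, the relevant cases are the obese ones. The target population is "predominantly male (60%), and 50% obese", so about 50 of 100. The starting standard error is √(1/50 + 1/50) = 0.200.
  - If 20% of the obese cases are removed: √(1/40 + 1/50) = 0.212, about 6% wider.
  - If all 20 removed cases are obese: √(1/30 + 1/50) = 0.231, about 15% wider.

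**The case against.** Several counter-arguments have force.

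- **The lists may not be complete.** Both say that the criteria include what follows, so further exclusions for cases are possible. This stands as a reason to say that the differences *can* include other illness. It does not close the gap, because a broad illness exclusion is written for controls and none for cases.
- **Renal disease is already excluded in cases.** True, and this removes an obvious other source of albuminuria. It does not cover diabetes, cardiac or liver disorders.
- **The effect is small.** On the 10-20% assumptions the bias is at most 0.6 standard errors, in a comparison with ten controls that is not the powered analysis. This stands and sets the priority.
- **Analysis populations can be left to the SAP.** The remedy partly belongs there, but the unequal eligibility rules are fixed in the protocol.

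Three stronger readings are tempting, and the protocol does not support them.

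- *The bias favours the hypothesis.* Hypotheses 1-3 concern associations of the peptide ratio with outcomes, not case-control differences. How other illness moves Ang II or Ang-(1-7) is not given. If Arm 2 children, who come from an obesity program or a gastroenterology clinic, have more liver disease, liver differences would shift the other way.
- *Both arms and every marker are affected alike.* The comparison is spelled out for Arm 1 only. Arm 2 has no echocardiogram, so any LVH contrast rests on ten children.
- *The differences do contain other illness.* The protocol reports no comorbidity in cases, so only the possibility follows from its text.

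**Conclusion.** The concern holds in a limited form. As worded, illness that does not cause hypertension can be present among cases and is barred among controls, and nothing stated in the protocol removes it from the unadjusted comparison with Arm 1. The 0.05-0.20 SD bias rests wholly on the assumed 10-20% share and 0.5-1 SD shift. With negligible comorbidity it is near zero, and its sign is not determined. For Arm 2 the point is weaker, and it is also unclear what the illness exclusion means for children drawn from those clinics. This is an inexpensive improvement to a supporting comparison and does not threaten the study's main analyses.

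**What to change.** 1. For the case-control comparisons, set one list of conditions other than hypertension and obesity (for example diabetes, structural heart disease, primary liver disease). Apply it identically to cases and controls, using the past medical history already collected. Let this list define the illness exclusion for controls, so that the open wording no longer bars a control for something permitted in a case.
2. Do not exempt a listed condition in cases because it is thought to result from hypertension or obesity. Exempting it in cases only would keep part of the asymmetry.
3. Keep all cases in the within-case models, and report the unrestricted case-control comparison as a sensitivity analysis.
4. Apply the same list to any comparison of obese cases with Arm 2, and state how the exclusion for significant medical problems applies to children from the obesity program and the gastroenterology clinic.

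**Cost:** agreeing the list and flagging records, with no new data collection. If 20 cases are removed, standard errors widen by about 1% against Arm 1. For about 50 obese cases against the 50 Arm 2 controls, the widening is about 6%, or up to 15% if all 20 removed cases were obese.

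### LVH and albuminuria are primary outcomes only as yes/no; using the values already measured would cost nothing to collect and recover much power, chiefly for LVH at one year

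*Protocol*

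**What the plan says.** All from the protocol.

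- **Outcomes.** The primary outcomes are blood pressure, left ventricular hypertrophy (LVH) and albuminuria, at baseline and after 12 months of treatment. LVH is a left ventricular mass index at or above the 95th "percentile for age and sex on echocardiography defines left ventricular hypertrophy, and a urinary albumin-to-creatinine ratio" above 30 mg/g "creatinine defines albuminuria". Neither underlying value is named as an outcome in its own right.
- **Blood Pressure Measurements.** Blood pressure is kept on a continuous scale: "we will standardize blood pressure with z scores", and "Ambulatory blood pressure index will be calculated as the mean divided by the 95th percentile".
- **Sample Size and Power.** With 100 subjects, blood pressure is planned through a correlation, with more than 90% "power to detect a correlation as low as 0.4 between Ang II and Ang-(1-7) and blood pressure". LVH is planned through an odds ratio: "the prevalence of left ventricular hypertrophy is 40-60% before and 10-20% after treatment", the Ang II:Ang-(1-7) ratio has a standard deviation (SD) of 8.4, and there is more than 90% "power to detect an odds ratio of 1.15 or higher both at baseline and at one year". Albuminuria, at 20-60% prevalence, is said to behave similarly.
- **Statistical Plan.** General linear and logistic models, Pearson or Spearman correlations and log transformation are all listed, with no model assigned to an outcome. The test level is two-sided 0.05.

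**The concern.** A cut-off discards how far each child lies from the threshold, and it discards most when few children lie beyond it. By the protocol's own estimate that is the situation for LVH after treatment. The 12-month assessment is as much a primary outcome as the baseline one, so an association as strong as the one planned for blood pressure could be missed for one-year LVH although the same echocardiograms would show it.

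The printed odds ratio adds to the risk of misreading. Without a unit, 1.15 looks like a small effect. Read per unit of the ratio it is a large one, so a null one-year LVH result could be over-read as excluding even weak associations.

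**Working it through.** **Inputs.** From Sample Size and Power: n = 100; r = 0.4 (blood pressure only); LVH prevalence p of 40-60% at baseline and 10-20% at one year; albuminuria 20-60%; predictor mean 7.7 and SD 8.4; odds ratio 1.15. From Statistical Plan: two-sided alpha 0.05. Assumed here: all 100 children are assessed at 12 months, and predictor and trait are bivariate normal unless stated.

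**1. The protocol's own figures.**

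*Blood pressure.* Fisher z: Φ(atanh(0.4)·√97 − 1.96) = Φ(4.172 − 1.96) = 98.7%. The stated figure holds.

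*LVH.* Read per unit of the ratio, the effect per SD is 8.4 × ln(1.15) = 1.174, an odds ratio of e^1.174 = 3.23 per SD. The usual formula for logistic regression on a continuous predictor is Φ(√(n·p(1−p)) × 1.174 − 1.96):
- p = 0.10: Φ(3 × 1.174 − 1.96) = 94.1%
- p = 0.15: 98.7%
- p = 0.20: Φ(4 × 1.174 − 1.96) = 99.7%
- p = 0.40-0.60: above 99.9%

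Read per SD instead, the same formula gives only 6-10%, so the per-unit reading is the intended one.

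*Simulation of that claim at p = 0.10, n = 100.* With a normal predictor, power is about 85-87% by the Wald test and 87-89% by the likelihood-ratio test. With a lognormal predictor (mean 7.7, SD 8.4) it is about 93%. At p = 0.20 both predictor shapes give 97-98%. The formula is thus slightly optimistic at the lowest prevalence, where power above 90% depends on the predictor's shape.

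**2. What the cut-off costs.** Dichotomising at prevalence p shrinks a correlation r to r·φ(z_p)/√(p(1−p)). The share of information kept is φ(z_p)²/(p(1−p)). The smallest correlation detectable with 90% power is tanh((1.96 + 1.2816)/√97) = 0.318 for the continuous value; dividing by φ(z_p)/√(p(1−p)) gives the yes/no figure.

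| p | Information kept | Smallest r at 90% power | Power at r = 0.4 |
|---|---|---|---|
| continuous | 100% | 0.32 | 98.7% |
| 0.10 | 34% | 0.54 | 65.1% |
| 0.15 | 43% | 0.49 | 75.0% |
| 0.20 | 49% | 0.45 | 80.9% |
| 0.40 or 0.60 | 62% | 0.40 | 89.6% |
| 0.50 | 64% | 0.40 | 90.3% |

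Worked line for p = 0.10: the shrunken correlation is 0.4 × √0.342 = 0.234, and Φ(atanh(0.234)·√97 − 1.96) = 65.1%.

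Simulation at r = 0.4 (20,000 runs; Wald to likelihood-ratio test) agrees: 62-66%, 74-76% and 80-82% at p = 0.10, 0.15 and 0.20, and 90-92% at 0.40-0.60, against 98.7% for the linear analysis.

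One-year LVH uses the rows 0.10-0.20, baseline LVH the rows 0.40-0.60, and albuminuria runs from 0.20 to 0.60 (81-90%).

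**3. Departures from normality (r = 0.4, 10,000 runs, p = 0.10 and 0.20).** Right-skewed errors: 35% and 60% yes/no against 98% linear. Heavy-tailed errors: 59% and 86% against 98%. Left-skewed errors reverse the picture: yes/no power is 98% and 99.6%. If albumin values pile up at the assay limit, Spearman power is 97% with 30% of values tied and about 95% with half tied, against 81% for yes/no at 20% prevalence.

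**The case against.** **The outcomes match the hypotheses.** Hypothesis 1 is about LVH and albuminuria as conditions, and the cut-offs define those conditions. This stands. It is why the categories should still be reported, and why this is an improvement and not a correction of an error.

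**r = 0.4 was never planned for LVH.** This also stands. The planned LVH effect, 3.23 per SD, corresponds to a latent correlation of about 1.174/√(1.174² + π²/3) = 0.54. Simulated at that value, yes/no power is 89-91% at 10% prevalence, 95-96% at 15% and 98% at 20%. A reader might infer from the 65-81% figures that the stated power is wrong or that LVH is underpowered as planned. The documents do not support that: those figures belong to a weaker association, used only as a common yardstick. The share of information lost does not depend on the yardstick.

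**The reach is limited.** A reader might also infer that both outcomes lose heavily at both times. They do not. Power at the yardstick falls well below 80% only for one-year LVH at about 10-15% prevalence.

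**Continuous analysis is not excluded.** The Statistical Plan already lists linear models, and an analysis plan that is not shown could use them. True, but the protocol itself fixes the primary outcomes and their power as yes/no, and no continuous LV mass or albumin outcome is named. Choosing one after seeing the data would be post hoc.

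**The gain depends on shape.** It presumes that the association also runs below the cut-offs, which the protocol does not state, and left-skewed errors would remove the advantage. That stands as a condition.

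**The missing unit is clerical.** Agreed: the adjacent SD lets a reader recover it.

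**Conclusion.** The point holds as a cheap improvement. The claim of more than 90% power for an odds ratio of 1.15 is reproduced by formula at every stated prevalence. It is borderline only at 10%, where simulation gives about 85-89% with a normal predictor and about 93% with a lognormal one, before any child is lost.

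The avoidable cost lies in the form of the outcome. Under a normal trait with 100 children assessed, the cut leaves one-year LVH with roughly a third to a half of the information. The association must then be about 1.4 to 1.7 times as strong to be found with 90% power (0.454/0.318 = 1.43; 0.543/0.318 = 1.71). For baseline LVH and most of the albuminuria range the gain from a continuous analysis is real but modest.

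The conclusion rests on the protocol's prevalence estimates, on approximate normality or right skew of the trait, and on an association that does not start only at the threshold.

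**What to change.** In Outcomes, name two continuous measures at baseline and 12 months as the form that carries the primary association test:
- LV mass index divided by its 95th percentile for age and sex, the same construction as the ambulatory blood pressure index;
- the natural log of the albumin-to-creatinine ratio.

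In the Statistical Plan, assign both to the general linear models already listed, with Spearman correlation if many albumin values lie at the assay limit. Report LVH and albuminuria as yes/no by logistic regression as supporting analyses. The continuous form should replace the yes/no form in the primary test and not be added to it, so that the number of primary tests does not grow.

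In Sample Size and Power, give the detectable correlation for the continuous measures (0.32 with 90% power at n = 100). State that the odds ratio of 1.15 is per unit of the ratio, about 3.2 per SD of 8.4, and note that power is close to 90% at 10% prevalence.

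Cost: wording only. The values and the percentile reference are already needed to apply the cut-offs, and every method is already in the plan. The downside is that the clinical categories named in the hypotheses carry less weight in the association test.
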